7.2 Classification of an Adverse Event

7.2.1 Severity of Event

The severity of each AE will be graded on a 3-point scale and reported in detail as indicated on the eCRF:

- **Mild:** awareness of sign or symptom but easily tolerated, causing minimal discomfort, and not interfering with normal everyday activities
- **Moderate:** sufficiently discomforting to interfere with normal everyday activities
- **Severe:** incapacitating and/or preventing normal everyday activities

7.2.2 Relationship to Study Drug

The causality of each AE should be assessed and classified by the Investigator as “related” or “not related.” An event is considered related if there is a reasonable possibility that the event may have been caused by the study drug under investigation (i.e., there are facts, evidence, or arguments to suggest possible causation).

Consider the following when assessing causality:

- Temporal associations between the agent and the event
- Response to cessation (de-challenge) or re-challenge
- Compatibility with known class effect
- Known effects of concomitant medications
- Pre-existing risk factors
- A plausible mechanism
- Concurrent illnesses

7.2.2.1 Duration

The start and stop dates for AEs will be recorded using the following criteria:

- **Start:** Date of the first episode of the AE or date of significant sustained worsening in severity
- **Stop:** Date when AE either ceased permanently or changed in severity

7.2.2.2 Frequency

The frequency of the AE should be indicated according to the following definitions:

- **Single:** Experienced once, without recurrence
- **Recurrent:** More than one discrete episode with the same severity

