NPI-NH psychosis score responder analyses also demonstrate the significant and clinically relevant treatment effect of pimavanserin 34 mg compared with placebo in subjects with ADP. Furthermore, defining responder as either a 30% or greater improvement or a 50% or greater improvement from Baseline NPI-NH psychosis score showed a significantly greater proportion of responders in the pimavanserin group (Table 1–2).

Table 1–2 NPI-NH Psychosis Score Percent Responder Analysis – Full Analysis Set – Week 6 (Day 43)

Treatment Group (% Responder)	Percent Improvement from Baseline				
	≥20%	≥30%	≥50%	≥75%	100%
Pimavanserin 34 mg	58.6%	55.2%	50.6%	27.6%	12.6%
Placebo	46.2%	37.4%	34.1%	16.5%	9.9%
p-value for test of group difference	0.0937	0.0159	0.0240	0.0656	0.5514

Source: ACP-103-019 Clinical Study Report

Note: Missing values were imputed as non-response

With respect to safety, pimavanserin appeared to be well-tolerated with no new safety observations in this elderly and frail patient population compared to the pimavanserin PDP safety database. An equal number of post-randomization deaths were reported: 4 deaths in the pimavanserin group and 4 in the placebo group.

There were more SAEs reported in pimavanserin group (16.7%) than in the placebo group (11.0%). A review of individual SAEs revealed a similar distribution of Medical Dictionary for Regulatory Activities (MedDRA) preferred terms between the two treatment groups with no clusters or common underlying mechanisms identified. However, there were fewer

discontinuations due to AEs in the pimavanserin group (8.9%) compared with the placebo group (12.1%).

The most frequently reported AEs in the pimavanserin group were fall (23.3%), urinary tract infection (22.2%), and agitation (21.1%). Agitation was reported more often in the pimavanserin group than in the placebo group.

The mean change from baseline in the QTc interval in subjects treated with pimavanserin was 9.4 ms at 12 weeks (Day 85) with no significant outliers reported at Day 85 (>500 ms or $\Delta \geq 60$ ms). One subject in the pimavanserin group and one subject in the placebo group had a $\Delta \geq 60$ ms at Day 15. Each subject continued in the study.

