9.5.4 Safety Analyses

All safety results will be summarized using descriptive statistics. Separate summaries will be provided for the open-label and double-blind periods. The double-blind summaries will be presented by treatment group. Adverse events will be classified into standard terminology using MedDRA. Adverse events may also be categorized into categories of special interest. Treatment-emergent AEs, TEAEs leading to discontinuation, TEAEs related to study drug, TEAEs by maximum severity, serious TEAEs, and serious TEAEs related to study drug will all be summarized. Other TEAEs of special interest may also be summarized.

Descriptive statistics for ECG, vital signs, GCAS, MMSE, ESRS-A total score and all subscales, and clinical laboratory parameters, including change from Baseline when applicable, will be tabulated by treatment group and timepoint. Additionally, categorical analyses will be conducted on the incidence of subjects with prolonged QTc intervals and changes in QTc intervals in accordance with ICH guidelines. The incidence of clinically significant changes in selected laboratory parameters will also be summarized.

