14.1 Adverse Events

All Adverse events (AEs) will be coded using MedDRA version 20.0 or newer.

An AE (classified by preferred term) will be considered a treatment emergent AE (TEAE) if the onset date was on or after the date of first dose of open-label pimavanserin and up to 30 days past the last dose of study drug. AEs reported on Day 1 based on open-label Baseline (pre-dose) findings (e.g. clinically significantly abnormal vital signs, laboratory test results, or electrocardiogram parameters) will not be considered as TEAEs.

Each TEAE will be assigned to either the open-label or double-blind period based on the onset date. For randomized subjects, if the onset date was on or after the date of first dose of double-blind study drug, the TEAE will be assigned to the double-blind period. All other TEAE will be assigned to the open label period.

The event counts and the number and percentage of subjects reporting TEAEs will be tabulated by SOC and preferred term; and, by SOC, preferred term, and maximum severity. If more than 1 AE occurs with the same preferred term for the same subject, the subject will be counted only once for that preferred term using the most severe occurrence for the

summarization by severity. In addition, the event counts and the number and percentage of subjects with TEAEs classified by the Investigators as related to the study drug, with most frequently reported TEAEs (preferred terms reported by $\geq 5\%$ of subjects overall for the open-label period and $\geq 5\%$ of subjects in either treatment group for the double-blind treatment period), with treatment emergent serious AEs, with fatal AEs (i.e. events that cause death), and with TEAEs leading to discontinuation of study drug will be summarized by SOC and preferred term. The display in these tables will be sorted alphabetically by SOC and then by descending subject frequency for the preferred terms using combined counts from both groups within each SOC. The event counts and the number and percentage of subjects with any TEAEs will also be tabulated by preferred term without SOCs. This table will be sorted by descending subject frequency using combined counts from all subjects.

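### An adverse event first seen on open-label drug and repeated at the same severity after randomization can be booked to the open-label period and so be missing from the by-arm double-blind tables

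*Protocol*

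**What the plan says.** **Protocol 7.2.2.1 (Duration).** The start of an adverse event is the "Date of the first episode of the AE or date of significant sustained worsening in severity". The stop is the "Date when AE either ceased permanently or changed in severity".

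**Protocol 7.2.2.2 (Frequency).** Single is kept for an event "Experienced once, without recurrence". Recurrent means "More than one discrete episode with the same severity".

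**SAP 14.1 (Adverse Events).** "Each TEAE will be assigned to either the open-label or double-blind period based on the onset date". For randomized subjects, onset on or after the first double-blind dose makes the event double-blind; then: "All other TEAE will be assigned to the open label period". The tables give event counts as well as numbers of subjects.

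**Presentation.** For the double-blind period, Protocol 9.5.4 says: "The double-blind summaries will be presented by treatment group". SAP 14 presents the open-label period for all subjects combined, by randomization status and by final dose, but not by randomized arm.

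The SAP 14.1 listing includes onset date, resolution date and frequency. Neither document asks for a date for each episode, splits a Recurrent record at the first double-blind dose, or counts such a record as double-blind when a later episode falls there.

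**The concern.** Every randomized subject has first taken pimavanserin for 12 weeks. Someone who falls in those weeks and is then randomized to continue or to stop is informative about whether the drug contributes, and Protocol 7.2.2 itself lists response to cessation among the causality considerations. If a later fall of the same severity is added to the earlier record, it contributes no subject and no event to the double-blind table of either arm. Since the open-label tables are not by arm, it then appears in no by-arm adverse event table.

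At stake is the randomized comparison of episodic harms such as falls and agitation. Protocol 1.3.2 reports fall as the most frequent event on pimavanserin in the earlier Alzheimer's disease psychosis study. The point concerns new episodes after randomization, not events still ongoing at Week 12.

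**Working it through.** **Tracing the rule.** The plan gives no figure to reproduce. Take a mild fall at Week 5 and another at Week 20, which is double-blind Week 8.

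1. Under 7.2.2.2 the fall has recurred, so it is not Single. Both episodes are mild, so Recurrent fits.
2. Under 7.2.2.1 the record starts at Week 5. It has neither ceased permanently nor changed in severity in between.
3. Under SAP 14.1 a Week 5 onset precedes the first double-blind dose, so the record is open-label.
4. The Week 20 fall adds nothing to the double-blind table.

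If the Week 20 fall were a significant sustained worsening, it would get a new start date and be counted. A milder repeat ends the old record, but 7.2.2.1 gives no explicit start rule for it. On event counts, five falls of one severity make one event, while one event that worsens makes two.

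**Illustrative size.** Inputs:

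- Fall incidence on pimavanserin of 23.3% (Protocol 1.3.2), taken as a 12-week incidence and assumed to apply here.
- Double-blind follow-up of 26 weeks.
- s, the share of repeats at the same severity: assumed 0.5 to 1.0, applied once per subject.

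*Constant hazard.* λ = −ln(1 − 0.233)/12 = 0.0221 per week. Double-blind incidence = 1 − exp(−0.0221 × 26) = 43.7%. Open-label and double-blind falls are independent, so the missing share is 0.233 × s.

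*Varying risk between subjects (gamma frailty, variance v).* S(t) = (1 + vλt)^(−1/v), with λ = [(1 − 0.233)^(−v) − 1]/(12v). Missing share = s × [1 − S(12) − S(26) + S(38)] / [1 − S(26)].

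| Model | All falls counted | Recorded, s = 0.5 | Recorded, s = 1 | Missing share |
|---|---|---|---|---|
| Constant hazard | 43.7% | 38.6% | 33.5% | 12–23% |
| v = 0.5 | 41.5% | 35.3% | 29.1% | 15–30% |
| v = 1 | 39.7% | 32.7% | 25.7% | 18–35% |
| v = 2 | 37.0% | 28.9% | 20.9% | 22–43% |

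*Shorter exposure.* The planned relapse rates (35% and 60%) and dropout rate (25%) in Protocol 9.3, taken as independent exponentials, give hazard h = [−ln(1 − relapse) − ln 0.75]/26 and mean exposure (1 − exp(−26h))/h. On pimavanserin this is 0.5125/0.02763 = 18.5 weeks; on placebo it is 0.70/0.04631 = 15.1 weeks. At 18.5 weeks with s = 1, the missing share is 23% (constant hazard), 36% (v = 1) and 45% (v = 2).

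**Effect on the comparison.** Under a constant hazard both arms are multiplied by (1 − 0.233s), so the risk ratio is unchanged. With an assumed double-blind hazard ratio of 1.5 over 26 weeks, the risks are 57.8% and 43.7%. The ratio is 1.32 before and after, while the difference of 14.1 points is recorded as 12.4 (s = 0.5) or 10.8 (s = 1).

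Under v = 1, s = 1 and a doubled rate on pimavanserin, at 18.5 and 15.1 weeks:

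- All falls counted: 31.9% v 16.0%, difference 15.9 points, ratio 1.99.
- Recorded: 20.3% v 9.8%, difference 10.5 points, ratio 2.07.

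Part of that difference comes from unequal follow-up. With 18.5 weeks in both arms it is 12.9 points, recorded as 8.6.

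**The case against.** The strongest objection is that merging is inferred from field definitions. Nothing instructs sites to attach a later fall to a resolved record. Protocol 7.4.1 requires all observed and reported events to be recorded, and asks at each visit about the time since the last one. Each event carries its own causality, action taken and outcome, and Recovered/resolved is an available outcome. SAP 14.1 allows for several events with one preferred term in a subject. A treated and cured infection would naturally be closed, so infections are a weak example. The eCRF completion guideline, which would settle this, is not among the documents. All of this stands, and it is why the point says *can be missing*. It does not remove the point, because the written definitions permit merging and sites may differ.

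A reader might also infer more than the documents support:

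- *That every recurring event is lost.* Only same-severity repeats of an event that began before the first double-blind dose are affected.
- *That the tables favour pimavanserin.* Randomization balances open-label history, and the risk ratio is roughly preserved above.
- *That the trial loses its only controlled safety evidence.* Laboratory tests, vital signs, ECG, GCAS, MMSE and ESRS-A are all summarized by arm in the double-blind period.
- *That events first seen in screening and repeated on drug are wrongly excluded.* Protocol 7.1.1 deliberately leaves out stable or intermittent chronic conditions that predate Baseline and do not worsen.

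The listing is a partial safeguard. It can identify Recurrent records that span randomization, but it cannot date the later episodes.

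**Conclusion.** The concern holds as a conditional one. Followed literally, the two documents together can drop same-severity repeat episodes after randomization from the by-arm double-blind tables and compress event counts. Absolute incidence and the risk difference are understated; the relative comparison is largely intact.

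The sizes are illustrations, not predictions: about 12–23% of subjects with a double-blind fall missing under a constant hazard, and up to about 45% with strong heterogeneity and every repeat at the same severity. They assume that sites merge episodes. They also carry over a fall rate from nursing-home subjects with a mean age of 85.9 years to clinic-attending subjects aged 50 to 90, and apply it to all randomized subjects although only Week 8 and Week 12 responders are randomized. The frailty variances, hazard ratios and s are assumptions.

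The primary endpoint is not affected. The correction is worth making because it is cheap and bears on the safety objective of comparing pimavanserin with placebo.

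**What to change.** In Protocol 7.2.2.1 and 7.2.2.2 and the eCRF completion guideline, have each discrete episode entered as its own adverse event with its own start and stop dates. As a minimum, require a new record, dated at the first episode on or after the first double-blind dose, whenever an event that began earlier recurs. If the eCRF cannot be restructured, add one date field to Recurrent records for that episode.

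In SAP 14.1, add a sentence that period assignment and event counts use that date, so that such a record counts as a double-blind event.

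The cost is a guideline change, one SAP sentence, somewhat more adverse event lines for sites and slightly higher reported counts.

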7.2.2.3 Action Taken with Study Drug

- **Dose reduced:** Study drug reduced
- **Dose increased:** Study drug increased
- **Dose not changed:** No change in study drug
- **Drug interrupted:** Study drug temporarily stopped
- **Drug withdrawn:** Study drug discontinued permanently

7.2.2.4 Therapy

- **None:** No new treatment instituted
- **Medication:** New treatment initiated as a direct result of AE
- **Other:** Other action required

7.2.2.5 Outcome

- **Recovered/resolved:** Recovered or resolved
- **Recovered/resolved with sequelae:** Recovered or resolved with sequelae
- **Not recovered/not resolved:** Not recovered or not resolved
- **Fatal:** Death related to AE
- **Unknown:** Unknown

7.2.2.6 Seriousness

- Not serious
- Serious

7.2.3 Definition of Unexpectedness

An AE, the nature or severity of which is not consistent with the information provided in the Reference Safety Information section of the current Pimavanserin Investigator's Brochure.

7.3 Time Period and Frequency for Event Assessment and Follow-up

In the event that a subject is withdrawn from the study because of an AE, the subject should be followed and treated by the Investigator until the AE has resolved, stabilized, or a new chronic baseline has been established.

7.4 Reporting Procedures

7.4.1 Adverse Event Reporting

The Investigator must record all observed AEs and all reported AEs. At each visit, the Investigator should ask the subject a nonspecific question (e.g., “Have you noticed anything different since your last visit?”) to assess whether any AEs have been experienced since the last report or visit.

Note that any use of medication (and specifically any newly prescribed medication) during the course of a study may indicate the occurrence of an AE that may need to be recorded on both the AE and the concomitant medication page.

All AEs will be coded by Data Management using MedDRA.

All AEs, serious and not serious, will be recorded on the AE eCRF page using appropriate medical terminology. Severity and relationship to study drug will be assessed by the Investigator as described above.

When possible, clinical AEs should be described by diagnosis and not by symptoms (e.g., “cold” or “seasonal allergies” instead of “runny nose”).

All AEs, *whether or not related to the study drug*, must be fully and completely documented on the AE eCRF and in the subject’s notes.

7.4.2 Serious Adverse Event Reporting

The reporting of SAEs by ACADIA to the Regulatory Authorities is a regulatory requirement. Each Regulatory Authority has established a timetable for reporting SAEs based upon established criteria.

Serious AEs and other reportable information must be reported within 24 hours of discovery to ACADIA or its designee. The SAE (initial and/or follow-up), pregnancy ([Section 7.4.3](#)), or overdose ([Section 7.4.4](#)) of study drug must be reported within 24 hours by completing the SAE, pregnancy, or overdose forms, as appropriate (details on how to report SAEs are provided in a separate study reference manual).

At a minimum, events identified by ACADIA to require expedited reporting as serious, unexpected, and related to study drug must be brought to the attention of the responsible institutional review board (IRB)/ethics committee (EC). For European Union member states, ACADIA or its designee will provide reports of suspected unexpected serious adverse reactions (SUSARs) directly to the ECs, as required by local legislation. In all other countries, it is the Investigator’s responsibility to provide these expedited reports to the responsible IRB/EC. It is also the Investigator’s responsibility to notify the responsible IRB/EC regarding any new and significant safety information.

For this study, sites will complete the paper overdose, SAE, and/or pregnancy form (for initial and/or follow-up information), including available supporting documentation relevant to the event and send (within 24 hours of discovery) to the contact numbers and/or email designated on the SAE form provided to the sites.

Subjects will be followed until Visit 17/ET for any SAEs and/or other reportable information or until such events have resolved or the Investigator, in conjunction with ACADIA, deems them to be chronic or stable.

In the event of any SAE (other than death), the study subject will be instructed to contact the Investigator (or designee) using the telephone number provided in the ICF. All subjects experiencing an SAE will be seen by the Investigator or designee as soon as is feasible following the report of the SAE.

SAEs should also be reported to the IRB/EC according to local regulations.

7.4.3 Reporting of Pregnancy

Any female subject who becomes pregnant during the study (with or without AEs) must be withdrawn from the study and the pregnancy must be reported on the pregnancy form. Any female subject who becomes pregnant during the study will be followed through the first well-baby visit.

Any AEs that are the consequence of pregnancy and which meet the criteria for serious should also be reported via the SAE form.

7.4.4 Reporting of Overdose

Any overdose ([Section 5.1.8](#)) must be reported within 24 hours by completing the overdose form. Any AEs that are associated with the event and which meet the criteria for SAEs should also be reported via the SAE form.

8 CLINICAL MONITORING

Routine monitoring of study sites is described in [Section 11](#).

Clinical site monitoring is conducted to ensure that the rights and well-being of human subjects are protected, that the reported study data are accurate, complete, and verifiable, and that the conduct of the study is in compliance with the currently approved protocol and amendment(s) as applicable, with GCP, and with applicable regulatory requirements. Details of the study site monitoring process are described in a separate clinical monitoring plan document.

9 STATISTICAL METHODS AND DATA ANALYSIS

9.1 Statistical and Analytical Plans

Statistical methods will be documented in detail in a statistical analysis plan to be approved by the Sponsor prior to unblinding for the interim analysis.

9.2 Statistical Hypotheses

The hypotheses for the primary endpoint are stated in terms of the hazard ratio, $HR = \lambda_{PIM} / \lambda_{PBO}$, where λ_{PIM} and λ_{PBO} denote the hazard rates of relapse for the pimavanserin treatment group and the placebo treatment group, respectively.

- The null hypothesis for the primary efficacy endpoint is: $HR = 1$
- The alternative hypothesis for the primary efficacy endpoint is: $HR \neq 1$

The hypotheses for the key secondary endpoint are stated in terms of the hazard ratio, $HR = \lambda_{PIM} / \lambda_{PBO}$, where λ_{PIM} and λ_{PBO} denote the hazard rates of discontinuation from the double-blind period for any reason (other than termination of the study by the Sponsor) for the pimavanserin treatment group and the placebo treatment group, respectively.

- The null hypothesis for the key secondary efficacy endpoint is: $HR = 1$
- The alternative hypothesis for the key secondary efficacy endpoint is: $HR \neq 1$

9.3 Sample Size Determination

This study will enroll approximately 356 subjects in order to randomize approximately 178 subjects with dementia-related psychosis who meet response criteria ([Section 3.3](#)).

The sample size calculation was based on the following assumptions: a placebo relapse event rate of 60% over 26 weeks; a pimavanserin relapse event rate of 35% over 26 weeks (hazard ratio = 0.47); a dropout rate of 25% over 26 weeks; an overall two-sided alpha level of 0.05; use of a one-sided (0.025) O'Brien-Fleming stopping boundary to adjust for a single interim analysis that will be performed when one half of the total planned number of post-randomization relapse events have occurred; and a power of 90%. The total number of post-randomization relapse events required at the final analysis is 75 and the calculated sample size is 89 in each of the two treatment groups (giving a total estimate of 178 subjects).

Study enrollment will be closed when approximately 178 subjects have been randomized in the double-blind period or when 75 adjudicated post-randomization relapse events have occurred. In the event that the randomization rate is lower than anticipated and/or the relapse event rate is lower than anticipated, the number enrolled and randomized may be increased up to a maximum of 400 randomized subjects in order to observe 75 post-randomization relapse events.

An interim efficacy analysis will be performed ([Section 9.5.8](#)), and the study may be terminated early if the interim analysis results meet prespecified stopping criteria.

